8.4.1.3 Secondary endpoints

Progression Free Survival

PFS (per RECIST 1.1 as assessed by the investigator) will be defined as the time from the date of randomization until the date of objective disease progression or death (by any cause in the absence of progression) regardless of whether the patient discontinues therapy or receives another anticancer therapy prior to progression (ie, date of event or censoring – date of randomization + 1). Patients who have not progressed or died at the time of analysis will be censored at the time of the latest date of assessment from their last evaluable RECIST 1.1 assessment. However, if the patient progresses or dies after 2 or more missed visits, the patient will be censored at the time of the latest evaluable RECIST 1.1 assessment prior to the 2 missed visits. If the patient has no evaluable visits or does

not have baseline data, they will be censored at Day 1 unless they die within 2 visits of baseline, then they will be treated as an event with date of death as the event date.

The PFS time will always be derived based on scan/assessment dates and not visit dates.

RECIST 1.1 assessments/scans contributing toward a particular visit may be performed on different dates. The following rules will be applied:

- For Investigator assessments, the date of progression will be determined based on the earliest of the RECIST 1.1 assessment/scan dates of the component that indicates progression.
- For BICR assessments, date of progression will be determined based on the earliest of the dates of the component that triggered the progression on the first set of scans that indicates progression for the adjudicated reviewer selecting PD, or of either reviewer where both reviewers select PD as a timepoint response, and there is no adjudication for central review (BICR) data.
- When censoring a patient for PFS, the patient will be censored at the latest of the dates contributing to a particular overall visit assessment.

Note: For target lesions, only the latest scan date is recorded out of all scans performed at that assessment for the target lesions, and similarly for non-target lesions, only the latest scan date is recorded out of all scans performed at that assessment for the non-target lesions.

A sensitivity analysis of PFS will be performed using BICR assessments according to RECIST 1.1.

Objective response rate

ORR (per RECIST 1.1 using investigator assessments) is defined as the number (%) of patients with at least 1 visit response of CR or PR. Data obtained up until progression, or the last evaluable assessment in the absence of progression, will be included in the

assessment of ORR. Patients who go off treatment without progression, receive a subsequent therapy, and then respond will not be included as responders in the ORR.

Duration of response

DoR (per RECIST 1.1 using investigator assessments) will be defined as the time from the date of first documented response until the first date of documented progression or death in the absence of disease progression (ie, date of PFS event or censoring – date of first response + 1). The end of response should coincide with the date of progression or death from any cause used for the RECIST 1.1 PFS endpoint.

The time of the initial response will be defined as the latest of the dates contributing toward the first visit response of CR or PR. If a patient does not progress following a response, then their DoR will be censored at the PFS censoring time. DoR will not be defined for those patients who do not have documented response.

Time from randomization to second progression (PFS2)

PFS2 will be defined as the time from the date of randomization to the earliest of the progression event subsequent to that used for the PFS endpoint or death. The date of second progression will be recorded by the Investigator in the eCRF and defined according to local standard clinical practice and may involve any of the following: objective radiological imaging, symptomatic progression, or death. Second progression status will be reviewed (every 6 weeks for the first 48 weeks relative to the date of randomization and then every 8 weeks thereafter) following the progression event used for the primary variable PFS (the first progression) and status recorded. Patients alive and for whom a second disease progression has not been observed should be censored at the last time known to be alive and without a second disease progression, that is, censored at the latest of the PFS or PFS2 assessment date if the patient has not had a second progression or death.

Time from randomization to the first subsequent therapy or death

Time to the first subsequent therapy (TFST) or death will be defined as the time from the date of randomization to the earlier of either the start date of the first subsequent anticancer therapy after discontinuation of randomized treatment or the date of death (ie, the date of first subsequent cancer therapy, death, or censoring defined as the date of randomization + 1 day). Any patient not known to have received a first subsequent anticancer therapy will be censored at the last date that the patient was known not to have received a first subsequent anticancer therapy. If a patient terminated the study before the first subsequent therapy for a reason other than death, the patient will be censored at the earliest of either the patient's last known date to be alive or the study termination date.

Time from randomization to the second subsequent therapy or death

As a supportive summary to PFS2, time to second subsequent therapy (TSST) or death will be defined as the time from the date of randomization to the earlier of either the start date of the second subsequent anticancer therapy after discontinuation of first subsequent therapy, or the date of death. Any patient not known to have had a second subsequent anticancer therapy will be censored at the last date when the patient was known not to have received a second subsequent anticancer therapy. If a patient terminated the study for

reason other than death before second subsequent anticancer therapy, the patient will be censored at the earliest of the last known to be alive and termination dates.

Proportion of patients alive and progression free at 6 and 12 months

The APF6 and APF12 will be defined as the Kaplan-Meier estimate of PFS (per RECIST 1.1 as assessed by the investigator) at 6 months and 12 months respectively.

Proportion of patients alive at 12, 18 and 24 months after randomization

The OS12, OS18 and OS24 will be defined as the Kaplan-Meier estimate of OS at 12, 18 and 24 months respectively after randomization.

Best objective response

Best objective response (BoR) is calculated based on the overall visit responses from each RECIST 1.1 assessment, as described in [Appendix E](#). It is the best response a patient has had during their time in the study up until RECIST 1.1 progression or the last evaluable assessment in the absence of RECIST 1.1 progression.

Categorization of BoR will be based on RECIST 1.1 ([Appendix E](#)) using the following response categories: CR, PR, SD, PD, and NE.

BoR will be determined programmatically based on RECIST 1.1 using all investigator assessments up until the first progression event. For patients whose progression event is death, BoR will be calculated based upon all evaluable RECIST 1.1 assessments prior to death.

For patients who die with no evaluable RECIST 1.1 assessments, if the death occurs ≤ 90 days (ie, $2 \times (6 \text{ weeks} \pm 3 \text{ days})$) after randomization, then BoR will be assigned to the progression (PD) category. For patients who die with no evaluable RECIST 1.1 assessments, if the death occurs >90 days (ie, $2 \times (6 \text{ weeks} \pm 3 \text{ days})$) after the date of randomization, then BoR will be assigned to the NE category.

Progression events that have been censored due to them being >90 days after the last evaluable assessment will not contribute to the BoR derivation.

Time to response

Time to response (per RECIST 1.1 as assessed by the investigator) is defined as the time from the date of randomization until the date of documented response. The date of documented response should coincide with that used for the RECIST 1.1 DoR endpoint.

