### 3.2.1 Primary endpoint (OS)

OS is defined as the time from the date of randomization until death due to any cause (i.e., date of death or censoring – date of randomization + 1). Any patient not known to have died at the time of analysis will be censored based on the last recorded date on which the patient was known to be alive (SUR\_DAT, recorded within the SURVIVE module of the eCRF).

Note: Survival calls will be made following the date of data cut-off for the analysis (these contacts should generally occur within 7 days of the data cut-off). If patients are confirmed to be alive or if the death date is post the data cut-off date, these patients will be censored at the date of data cut-off. Death dates may be found by checking publicly available death registries (as applicable under local laws).

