### **3.2.7 Time from randomization to the first subsequent therapy or death (TFST)**

Time to the first subsequent therapy (TFST) or death will be defined as the time from the date of randomization to the earlier of either the start date of the first subsequent anticancer therapy after discontinuation of randomized treatment or the date of death (i.e., the date of first subsequent cancer therapy, death, or censoring defined as the date of randomization + 1 day). Any patient not known to have received a first subsequent anticancer therapy will be censored at the last date that the patient was known not to have received a first subsequent anticancer therapy. If a patient terminated the study before the first subsequent therapy for a reason other than death, the patient will be censored at the earliest of either the patient's last known date to be alive or the study termination date.

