### **3.2.9 Time from randomization to second progression-free survival (PFS2)**

PFS2 will be defined as the time from the date of randomization to the earliest of the progression event subsequent to first subsequent therapy (TFST) or death. Note the patient does not need to remain on their second treatment for the progression event to occur. The date of second progression will be recorded by the Investigator in the eCRF (PFS2 CRF) and defined according to local standard clinical practice and may involve any of the following: objective radiological imaging, symptomatic progression, or death. Second progression status will be reviewed (every 6 weeks for the first 24 weeks relative to the date of randomization and then every 8 weeks thereafter) following the progression event used for the primary

variable PFS (the first progression) and status recorded. Patients alive and for whom a second disease progression has not been observed should be censored at the later of the date of assessment on the PFS2 form indicating no progression (PFSRESP=2) or at the date of the last evaluable RECIST assessment (or day 1 if no post-baseline RECIST data is available; date of withdrawal, date last known alive, DCO or, if a patient has not had a first subsequent therapy; the date last known not to have received a first subsequent therapy (TFST censoring date).

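### The TFST time formula has lost its subtraction, and the TFST and TSST censoring sentences are not limited to patients who are alive

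*Protocol*

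**What the plan says.** Protocol 8.4.1.3 and SAP 3.2.7 carry the same TFST paragraph, in four parts:

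1. Event: time runs from randomization "to the earlier of either the start date of the first subsequent anticancer therapy after discontinuation of randomized treatment or the date of death".
2. Explanatory bracket: "the date of first subsequent cancer therapy, death, or censoring defined as the date of randomization + 1 day".
3. Censoring: "Any patient not known to have received a first subsequent anticancer therapy will be censored at the last date" on which the absence of such therapy was established.
4. Early termination: "If a patient terminated the study before the first subsequent therapy for a reason other than death", censoring is at the earlier of the last-known-alive date and the termination date.

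TSST (Protocol 8.4.1.3, SAP 3.2.8) has parts 1, 3 and 4 with the second subsequent therapy in place of the first. It has no bracketed formula.

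Both endpoints are secondary outcome measures in the PD-L1 TC/IC high subgroup and in all-comers (Protocol 2.2, SAP Table 2). Each is analysed by stratified log-rank test with an HR and 95% CI (Protocol 8.5.2.8 and Table 15, SAP 4.2.9 and Table 12). The methods sections describe this analysis as supportive, and SAP 4.1 confines formal testing to OS.

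**The concern.** The paragraph is the derivation rule from which the TFST dataset is built, and two of its parts disagree with the rest.

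First, nothing is subtracted in the bracket, so it is not a duration. Its plain reading is a censoring date of randomization plus one day, and part 3 gives a different date. Patients still event-free at the data cut-off would leave the risk set at once instead of contributing their follow-up.

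Second, part 3 applies to every patient without known subsequent therapy and does not exclude those who have died. Taken alone, it censors a patient who died untreated, although part 1 makes that death an event. The TSST sentence has the same gap. Under that reading the composite becomes a cause-specific time to therapy, with death as a censoring event.

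Because the SAP repeats the protocol text, the document used for programming does not settle either question.

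**Working it through.** **Step 1: the bracket against its sibling formulas.**

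| Endpoint | Where | Form |
|---|---|---|
| OS | SAP 3.2.1 | "date of death or censoring – date of randomization + 1" |
| PFS | Protocol 8.4.1.3 (same in SAP 3.2.1.1) | "date of event or censoring – date of randomization + 1" |
| Duration of response | Protocol 8.4.1.3, SAP 3.2.3 | PFS event or censoring date, minus first response date, plus 1 |
| TFST | Protocol 8.4.1.3, SAP 3.2.7 | "censoring defined as the date of randomization + 1 day" |

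The first three are date minus date plus 1. In TFST the minus sign has been replaced by words that turn the expression into a definition of censoring.

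**Step 2: the censoring sentence against its siblings.** PFS censors only patients who have neither progressed nor died, and PFS2 censors only patients who are alive (Protocol 8.4.1.3, SAP 3.2.9). The TFST and TSST sentences carry no such limit.

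**Step 3: possible size.** The plan states no event count, HR or power for TFST or TSST, so there is no figure to reproduce. What follows is an illustration on assumed inputs: constant monthly hazards λT (subsequent therapy) and λD (death without it) in the SoC arm, cause-specific HRs rT and rD for the experimental arm, and administrative censoring uniform between 23.6 and 40.6 months. The two follow-up limits come from Protocol 8.2; everything else is assumed. It uses 100,000 simulated patients per arm and an unstratified Cox model.

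With constant hazards the two main quantities have closed forms:

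- Intended composite: HR = (λT·rT + λD·rD) / (λT + λD).
- Untreated deaths censored at death: HR = rT.

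They agree only when rT = rD. For λT = λD = 0.06, rT = 0.6 and rD = 0.9, the composite is (0.036 + 0.054) / 0.12 = 0.75, and with deaths censored the HR is 0.60. Swapping the effects gives 0.75 and 0.90. The simulation matches:

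| rT, rD (λT = λD = 0.06) | Intended composite | Untreated deaths censored | Event-free patients censored at Day 1, deaths kept as events |
|---|---|---|---|
| 0.7, 0.7 | 0.70 | 0.70 | 0.77 |
| 0.6, 0.9 | 0.75 | 0.60 | 0.81 |
| 0.9, 0.6 | 0.75 | 0.90 | 0.81 |
| 0.7, 1.0 | 0.85 | 0.69 | 0.88 |
| 1.0, 1.0 | 0.99 | 0.99 | 0.99 |

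Two other SoC hazard mixes were run (λT/λD of 0.08/0.04 and 0.04/0.08). The largest shifts from censoring deaths came with 0.04/0.08: 0.80 to 0.60 for (0.6, 0.9), and 0.70 to 0.91 for (0.9, 0.6).

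So Day-1 censoring pulls the HR towards 1 when there is an effect and leaves it alone when there is none. Censoring untreated deaths can move it either way or not at all. The closed forms apply to TSST with the second therapy in place of the first; TSST was not simulated.

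**The case against.** The strongest reply is that this is a typing error whose intent is plain. The bracket restates the sentence before it. Since it lists therapy, death and censoring together, the faulty words could attach to all three, which would be absurd. SAP 3.2.9 identifies the intended date directly: "the date last known not to have received a first subsequent therapy (TFST censoring date". Deaths are events on any fair reading, because the section titles, the lead sentence, the early-termination exception and the methods sections all say so. A patient who has died already has an event, so the censoring sentence is naturally read as covering the others.

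All of that stands as evidence of intent. It makes the point a drafting error, not a deliberate analysis choice. It does not make the text correct. The same wording sits in both governing documents. Day-1 censoring is also a real rule elsewhere in this plan, for PFS patients with no evaluable visits, so a programmer could not dismiss the bracket as impossible. Recovering the rule means overriding one clause by reference to other sections, and two programmers could resolve it differently.

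The reply also correctly limits any claim about PFS2. A reader might infer that a faulty TFST censoring date carries into PFS2, because SAP 3.2.9 uses it. The documents do not support that: 3.2.9 describes the date as the last one known to be free of therapy, not Day 1, and its rule covers only living patients.

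**Conclusion.** The TFST formula is wrong as written in both documents, and the TFST and TSST censoring sentences need a limit to patients who are alive. If programmed literally, the text could distort the TFST HR and, through the death-censoring wording alone, the TSST HR. The amount and direction depend on arm-specific rates of subsequent therapy and untreated death that the documents do not give. The figures above show what is possible under assumed constant hazards; they are not predictions for this trial.

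Two stronger readings are tempting and should not be drawn:

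- That the plan *will* bias the TFST HR. This requires one clause to be programmed against the explicit event definition. Even then, censoring deaths changes nothing when the effects on therapy and on death are equal.
- That Day-1 censoring erases the treatment effect. One can construct this: with 86 patients per arm, a SoC median of 8 months, and a monotherapy arm identical except for 12% long-term event-free patients, the HR goes from about 0.74 to about 1.00. But that model places the whole difference between arms in the patients whom the rule discards, so the result is built in. Under proportional effects the shift is 0.70 to 0.77.

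TFST and TSST are supportive and outside the multiple testing procedure. The primary OS analysis and its type I error are unaffected.

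**What to change.** Make these edits in both documents:

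- **TFST bracket (Protocol 8.4.1.3, SAP 3.2.7):** replace it with *date of first subsequent anticancer therapy, death or censoring – date of randomization + 1*.
- **TFST censoring sentence (same sections):** begin it *Any patient who is alive and not known to have received a first subsequent anticancer therapy will be censored at*, and leave the rest unchanged.
- **TSST censoring sentence (Protocol 8.4.1.3, SAP 3.2.8):** make the same insertion, with *second* for *first*. TSST has no bracket, so nothing else changes there.

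That is six text edits: two brackets and four sentences. No new data or analyses are needed, and the wording follows conventions the plan already uses for OS, PFS and PFS2. The programming specification for both endpoints should be checked against the corrected text.

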8.4.2 Calculation or derivation of safety variables

8.4.2.1 Adverse events

Safety and tolerability will be assessed in terms of AEs (including SAEs), deaths, laboratory data, vital signs, ECGs, and exposure. These will be collected for all patients. Data from all cycles of treatment will be combined in the presentation of safety data. “On treatment” will be defined as assessments between date of start dose and 90 days following discontinuation of IP (ie, the last dose of MEDI4736 + tremelimumab combination therapy or MEDI4736 monotherapy). For AEs, on treatment (or treatment-emergent AEs) will be

defined as any AEs that started after dosing or prior to dosing and which worsens following exposure to the treatment.

SAS will be used for reporting of safety data.

A separate data listing of AEs occurring more than 90 days after discontinuation of IP will be produced. These events will not be included in AE summaries.

8.4.2.2 Safety assessments

For the change from baseline summaries for vital signs, laboratory data, ECGs, and physical examinations, the baseline value will be the latest result obtained prior to the start of study treatment.

QTcF will be derived during creation of the reporting database using the reported ECG values (RR and QT) using the following formula:

$QTcF = QT/RR^{(1/3)}$ where RR is in seconds

Corrected calcium product will be derived during creation of the reporting database using the following formulas:

$Corrected\ calcium\ (mmol/L) = Total\ calcium\ (mmol/L) + ([40 - albumin\ (G/L)] \times 0.02)$

The denominator used in laboratory summaries will only include evaluable patients, ie, those who had sufficient data to have the possibility of an abnormality.

For example:

- If a CTCAE criterion involves a change from baseline, evaluable patients would have both a pre-dose and at least 1 post-dose value recorded.
- If a CTCAE criterion does not consider changes from baseline to be evaluable, the patient need only have 1 post-dose value recorded.

The denominator in vital signs data should include only those patients with recorded data.

8.4.3 Calculation or derivation of patient-reported outcome variables

PRO questionnaires will be assessed using the EORTC QLQ-C30 and EORTC QLQ-H&N35. All items/questionnaires will be scored according to published scoring guidelines. All PRO analyses will be based on the FAS.

8.4.3.1 EORTC QLQ-C30

The EORTC QLQ-C30 consists of 30 questions that can be combined to produce 5 functional scales (physical, role, cognitive, emotional, and social), 3 symptom scales (fatigue, pain, and nausea/vomiting), and a global measure of health status. The EORTC QLQ-C30 will be scored according to the EORTC QLQ-C30 scoring manual ([Fayers et al 1999](#)). An outcome variable consisting of a score from 0 to 100 will be derived for each of the symptom scales, each of the functional scales, and the global health status scale in the EORTC QLQ-C30 according to the EORTC QLQ-C30 Scoring Manual. Higher scores on

the global health status and functioning scales indicate better health status/function, but higher scores on symptom scales represent greater symptom severity.

The change from baseline in HRQoL will be assessed using the EORTC QLQ-C30 global QoL scale, which includes 2 items from the EORTC QLQ-C30: “How would you rate your overall health during the past week? (Item 29) and “How would you rate your overall QoL during the past week? (Item 30).”

Definition of clinically meaningful changes

Changes in score compared with baseline will be evaluated. A minimum clinically meaningful change is defined as an absolute change in the score from baseline of ≥ 10 for scales from the EORTC QLQ-C30 (Osoba et al 1998). For example, a clinically meaningful improvement in physical function (as assessed by EORTC QLQ-C30) is defined as an increase in the score from baseline of ≥ 10 , whereas a clinically meaningful deterioration is defined as a decrease in the score from baseline of ≥ 10 . At each post-baseline assessment, the change in symptoms/functioning from baseline will be categorized as improvement, no change or deterioration as shown in Table 3.

Table 13 Mean change and visit response in health-related quality of life

Score	Change from baseline	Visit response
EORTC QLQ-C30 Global quality of life score	$\geq +10$	Improvement
	≥ -10	Deterioration
	Otherwise	No change
EORTC QLQ-C30 symptom scales	$\geq +10$	Deterioration
	≤ -10	Improvement
	Otherwise	No change
EORTC QLQ-C30 functional scales	$\geq +10$	Improvement
	≥ -10	Deterioration
	Otherwise	No change

EORTC European Organisation for Research and Treatment of Cancer; QLQ-C30 30-item core quality of life questionnaire.

For each subscale, if $< 50\%$ of the subscale items are missing, then the subscale score will be divided by the number of non-missing items and multiplied by the total number of items on the subscales (Fayers et al 1999). If at least 50% of the items are missing, then that subscale will be treated as missing. Missing single items are treated as missing. The reason for any missing questionnaire will be identified and recorded. If there is evidence that the missing data are systematic, missing values will be handled to ensure that any possible bias is minimized.

Time to symptom deterioration

For each of the symptoms scales in the EORTC QLQ-C30, time to symptom deterioration will be defined as the time from randomization until the date of the first clinically meaningful symptom deterioration (an increase in the score from baseline of ≥ 10) or death

(by any cause) in the absence of a clinically meaningful symptom deterioration, regardless of whether the patient discontinues study treatment or receives another anticancer therapy prior to symptom deterioration. Death will be included as an event only if the death occurs within 2 visits of the last PRO assessment where the symptom change could be evaluated.

Patients whose symptoms (as measured by EORTC QLQ-C30) have not shown a clinically meaningful deterioration and who are alive at the time of the analysis will be censored at the time of their last PRO assessment where the symptom could be evaluated. Also, if symptoms deteriorate after 2 or more missed PRO assessment visits or the patient dies after 2 or more missed PRO assessment visits, the patient will be censored at the time of the last PRO assessment where the symptom could be evaluated. If a patient has no evaluable visits or does not have baseline data they will be censored at 0 days. The population for the analysis of time to symptom deterioration will include a subset of the FAS who have baseline scores of ≤ 90 .

Time to quality of life/function deterioration

For QoL, time to deterioration will be defined as the time from the date of randomization until the date of the first clinically meaningful deterioration (a decrease in the function scales or the global health status/QoL from baseline of ≥ 10) or death (by any cause) in the absence of a clinically meaningful deterioration, regardless of whether the patient discontinues study treatment or receives another anticancer therapy prior to QoL/function deterioration. Death will be included as an event only if the death occurs within 2 visits of the last PRO assessment where the QoL/function change could be evaluated.

Patients whose QoL (as measured by EORTC QLQ-C30) have not shown a clinically meaningful deterioration and who are alive at the time of the analysis will be censored at the time of their last PRO assessment where the QoL/function could be evaluated. Also, if QoL deteriorates after 2 or more missed PRO assessment visits or the patient dies after 2 or more missed PRO assessment visits, the patient will be censored at the time of the last PRO assessment where QoL/function could be evaluated. If a patient has no evaluable visits or does not have baseline data they will be censored at 0 days. The population for the analysis of time to QoL/function deterioration will include a subset of the FAS who have baseline scores of ≥ 10 .

Symptom improvement rate

The symptom improvement rate will be defined as the number (%) of patients with 2 consecutive assessments at least 14 days apart that show a clinically meaningful improvement (a decrease from baseline score ≥ 10 for EORTC QLQ-C30 symptom scales) in that symptom from baseline. The denominator will consist of a subset of the FAS who have a baseline symptom score ≥ 10 .

QoL/function improvement rate

The QoL/function improvement rate will be defined as the number (%) of patients with 2 consecutive assessments at least 14 days apart that show a clinically meaningful improvement (an increase from baseline score ≥ 10 for EORTC QLQ-C30 functional scales and global health status/QoL) in that scale from baseline. The denominator will consist of a subset of the FAS who have a baseline QoL/function score ≥ 10 .

